### 15.3 POPULATIONS FOR ANALYSES & GENERAL APPROACH (R33)

The primary analysis for the R33 Randomized Hybrid Effectiveness-Implementation Trial will use an intent-to-treat (ITT) approach with all enrolled subjects included in the analysis. Per-protocol analysis including only participants compliant with study protocols will be conducted as a secondary analysis. Secondary analyses are exploratory and will not be corrected for multiple comparisons. We will use hierarchical linear mixed model regression analyses to account for repeated measures within trial participants (the unit of randomization) in addition to the clustering of individuals within classes when receiving the experimental or control interventions. Missing data analyses will be informed by the pattern and reasons for missing data and will include multiple imputation (data missing at random) and sensitivity analyses using pattern mixture models (data not missing at random), if appropriate. This approach has been applied in previous trials by the investigators and highlighted as an exemplar in Annals of Internal Medicine.

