#### 15.4.2 R33 RANDOMIZED HYBRID EFFECTIVENESS-IMPLEMENTATION TRIAL

##### Primary Analysis

For the primary analysis, we will use mean PEG during follow-up (at 2, 4, and 6 months) as the outcome. The effect of treatment will be assessed using a hierarchical linear mixed model with fixed effects for treatment and baseline PEG and random effects for individual and class. In addition, we will test for evidence of an interaction between time and treatment by fitting a mixed model with an interaction between the treatment group indicator and follow-up time (viewed as a categorical random variable) and using a likelihood ratio test to assess whether the interaction terms are jointly significant. The results of this analysis will inform the interpretation of the primary analysis and guide secondary analyses. Analyses will be carried out using the statistical software R.

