##### Secondary Analyses

**Responder Analyses:** We will derive responder categories for our primary outcome of pain intensity and interference (PEG) at 2, 4, and 6 months corresponding to reductions from baseline of 30% (minimal improvement), 50% (moderate improvement), 75% and 100% (substantial improvement). Then, we will fit proportional odds models to assess the effect of treatment on the probability of falling into each of these categories. In addition, we will conduct cumulative responder analyses to assess the proportion of responders for all possible levels of pain intensity and interference reduction (0 to 100% reduction).

**Secondary Outcomes:** Secondary numerical outcome measures (e.g., self-efficacy, life satisfaction, physical functioning) will be analyzed similarly to the primary PEG outcome. Generalized linear mixed models will be used for binary and count outcomes.

**Longitudinal Analyses:** Systematic reviews and meta-analyses of interventions for chronic pain and chronic back pain commonly use short-, medium-, and long-term treatment effects for analysis. Therefore, in addition to the analyses of primary and secondary outcomes which provide a measure of cumulative burden over the six-month study period, we will conduct longitudinal analyses with time coded as a categorical variable to quantify group differences in primary and secondary outcomes at 2, 4, and 6 months. Differences in numerical outcomes will be assessed using linear mixed models as described above. Differences in categorical outcomes (e.g., Graded Chronic Pain Scale, health care use) will be assessed using multi-level mixed effects generalized linear models.

**Effect Heterogeneity Analyses:** While it remains important to estimate the overall (mean) effect of an intervention, analyses of intervention studies have increasingly focused on characterizing how population subgroups experience differential treatment effects. Here, we will employ modern statistical machine learning methods (including some co-developed by co-I [name]) to describe how disparity factors (i.e. race, ethnicity, income, wealth, education, health care access) interact to influence how responsive individuals are to treatment. These flexible methods combining matching techniques

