with decision trees will allow us to carry out a formal statistical test for effect heterogeneity, and (in the presence of heterogeneity) also yield simple classification rules that partition the population according to their expected treatment effect. In previous work, we have successfully applied these techniques to randomized trials with fewer participants (n=180) than we will have in this study (n=376) so we anticipate that we will have an adequate sample size to achieve meaningful results. For these analyses, we will use a limited set of outcomes (e.g., PEG, self-efficacy) at 2, 4, and 6 months to characterize the treatment effect. All analyses are exploratory and will not be corrected for multiple comparisons.

**Mediation Analyses:** In addition to characterizing how treatment effects vary across individuals, we will also explore the potential mechanisms driving these treatment effects via mediation analysis. Specifically, we will apply established methods to characterize the proportion of treatment effect for changes in pain intensity and interference at months 4 and 6 that can be explained by changes in self-efficacy, interoceptive awareness, and domain-specific life satisfaction measured in prior months. Mediation models will be estimated using the *mediation* package in R. Further, we will apply decomposition methods to understand whether the relationship between treatment effects and self-efficacy/life satisfaction is driven by mediation, moderation, or moderated mediation.

**Comparisons to Back Pain Populations with Low Health Disparities:** To assess the impact of Partners4Pain on mitigating disparities in pain self-management, we will compare findings to results from studies assessing self-management programs for chronic back pain with low PEHD representation, including studies from the HEAL initiative. This includes studies by our team assessing the impact of self-management for chronic neck and back pain. We will assess the similarity of mean outcome levels at baseline, treatment effects, drivers of effect heterogeneity, and mediating variables. Where possible, we will combine individual-level data (from previous studies conducted by our team) to formally test differences across studies.

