**Implementation and Disparity Mitigating Outcome Analyses:** Qualitative measures will be analyzed using methods described previously (see R61 Aims 1 & 2). Quantitative measures will be summarized and compared between treatment groups using two-sample t-tests (for continuous measures) and chi-square tests (for categorical measures). Exploratory analyses will employ regression and decision tree models to investigate the impact of disparity factors (i.e., race, ethnicity, income, wealth, education, health care access) on measures of program implementation.

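### Section 15.4.2 compares participant-reported implementation measures between arms with t-tests and chi-square tests that ignore clustering by class

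*Combined protocol and SAP*

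**What the plan says.** The paragraph on implementation and disparity-mitigating outcomes in Section 15.4.2 states: "Quantitative measures will be summarized and compared between treatment groups using two-sample t-tests (for continuous measures) and chi-square tests (for categorical measures". It mentions no class term.

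Elsewhere the R33 plan treats class as a source of correlation:

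- Section 15.3 sets the general approach: mixed models that handle repeated measures "in addition to the clustering of individuals within classes when receiving the experimental or control interventions".
- The primary analysis in 15.4.2 is a "hierarchical linear mixed model with fixed effects for treatment and baseline PEG and random effects for individual and class".
- Numerical secondary outcomes follow the primary model, and "Generalized linear mixed models will be used for binary and count outcomes".
- The power simulation in 15.2.2 builds in an intra-class correlation (ICC) of 0.05 for the PEG.

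Other relevant facts:

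- **Class size:** 7 to 16 per group in both arms (Table 5).
- **Randomization:** stratified by session offering (10.3).
- **Timing:** follow-up is counted from the start of the groups (13.4). Table 6 places the COM survey and the supportive environment and relational alliance survey at month 2, and satisfaction with and use of program activities at months 2, 4 and 6.
- **Status:** R33 Aim 3 is worded as description (6.2), and 15.3 says "Secondary analyses are exploratory and will not be corrected for multiple comparisons".

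**The concern.** A two-sample t-test and a chi-square test both assume independent participants. People taught for nine weeks in the same class, by the same facilitator and with the same classmates, may answer alike when asked how well the program met their needs. If so, the effective sample size is smaller than the head count, the standard error is too small and the p-value too low. An apparent difference between arms could then reflect a few unusually good or poor classes.

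The general statement in 15.3 does not settle the matter. The implementation paragraph is more specific and names its tests, so an analyst following it would leave class out.

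Measures taken before classes start are not affected, nor are flow data on organizations or facilitators. The items on use of and satisfaction with program activities are affected only if they are compared between arms. The documents do not say which items are, and program content differs in part by arm.

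**Working it through.** **1. The plan's own figures.** The plan gives no error rate, ICC or power for these comparisons. The related planning figures in 15.2.2 reproduce: 300 / (1 − 0.20) = 375, and 376 is the next even number; 0.9 / 2.5 = 0.36.

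**2. Inputs.**

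- From the documents: classes of 7 to 16 (Table 5); loss of up to 20%, total 376 and PEG ICC 0.05 (15.2.2); stratification by session offering (10.3).
- Assumed: two-sided 5% level; 20% loss at the assessment; one class per arm in each offering; the ICC of these measures, varied from 0.01 to 0.10; and the share s of that correlation due to session offering, set at none, half or all.

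**3. Formula.** Let m be the number analysed per class. An offering effect common to both arms cancels from the arm difference, but the t-test still counts it as noise. The true variance of the difference, relative to the variance the test uses, is

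D = 1 + (m − 1) × ICC − s × m × ICC

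and the actual type I error is 2 × [1 − Φ(1.96 / √D)].

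With 20% loss, classes of 7, 10, 13 and 16 give m = 5.6, 8, 10.4 and 12.8. At ICC 0.05:

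| Share due to offering | 7 enrolled | 10 | 13 | 16 |
|---|---|---|---|---|
| None: D | 1.23 | 1.35 | 1.47 | 1.59 |
| None: type I error | 7.7% | 9.2% | 10.6% | 12.0% |
| Half: type I error | 6.0% | 6.8% | 7.5% | 8.2% |
| All (D = 0.95): type I error | 4.4% | 4.4% | 4.4% | 4.4% |

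With no loss and nothing shared, classes of 7, 10 and 16 give 8.6%, 10.4% and 13.8%.

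**4. Simulated t-test, no treatment effect.** Classes per arm were 27 of 7, 19 of 10, 14 of 13 and 12 of 16 (182 to 192 enrolled per arm). Each participant was lost with probability 0.2. There were 20,000 data sets per cell, for a Monte Carlo standard error of about 0.2 points.

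| ICC | None shared: 7 / 10 / 13 / 16 | Half shared, range |
|---|---|---|
| 0.01 | 5.7 / 5.7 / 6.0 / 6.3% | 5.0–5.7% |
| 0.02 | 6.0 / 6.7 / 7.3 / 8.0% | 5.4–6.5% |
| 0.05 | 7.8 / 9.7 / 10.4 / 12.4% | 6.1–8.1% |
| 0.10 | 10.6 / 13.7 / 16.8 / 18.7% | 7.4–11.6% |

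With all of the correlation shared, the rate is 4.1% to 5.1% across these ICCs, so there is no inflation.

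**5. Simulated chi-square test.** This assumes 75% positive responses, correlation on the binary scale, and none shared. At ICC 0.05 the uncorrected test gives 7.7%, 9.4%, 10.6% and 12.2% for classes of 7, 10, 13 and 16. With the Yates correction it gives 5.8%, 7.4%, 8.4% and 9.8%. At ICC 0.02 the ranges are 6.0–7.9% uncorrected and 4.5–5.9% with Yates. If the 0.05 sits on a latent scale instead, the rates are about 7–10% and 5–8%.

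**6. Alternatives using class means (continuous measures).** A t-test on class means paired by offering gives 4.7% to 5.2% in every setting. The unpaired version gives 4.7% to 5.3% with none shared. At ICC 0.05 it falls to 2.9–3.5% with half shared and 1.4–2.7% with all shared.

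**The case against.** **Little depends on these p-values.** Aim 3 describes, the analyses are exploratory, no decision rule uses the results, and R33 is a later phase whose protocol still goes to the funder. This stands and limits the point to minor. It does not make the standard errors right: leaving out a multiplicity correction concerns how many tests are run, not whether each is valid.

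**The 8–12% figure depends on its assumptions.** It borrows an ICC planned for the PEG, informed by back pain intensity in another trial's control arm, and assumes offering explains nothing. This stands as a limit on the number. The figure is not a bound: a lower ICC, sharing through offering or a Yates correction lowers it, and fuller classes raise it.

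**The alliance survey rates the study team.** Section 14.2.3 does not say that it rates the class or its facilitator, so answers may cluster less by class. This stands in part. The COM survey, which asks whether the program met participants' needs, is the clearer case.

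**Other analyses are also silent on class.** For the responder analysis, "we will fit proportional odds models to assess the effect of treatment on the probability of falling into each of these categories"; the heterogeneity analysis will "carry out a formal statistical test for effect heterogeneity". Neither mentions class, and nor does the mediation analysis. That is true, but there the detail is merely missing, and a class term could be added within what is written. The implementation paragraph names tests that have no place for one.

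**A model with session offering and between-class degrees of freedom asks more than the primary model does.** This is fair. The class random effect alone removes the inconsistency; the rest is refinement.

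**Conclusion.** The concern holds, as a minor point. For participant-reported measures collected after classes begin, the named tests conflict with the plan's own treatment of class and give p-values that are too low whenever classmates correlate beyond a shared offering effect.

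The size is unknown because no ICC is given for these measures. It runs from no inflation, if session offering carries all the correlation, to about 8–12% for the t-test if it carries none. That upper range assumes ICC 0.05, classes of 7 to 16, 20% loss and a two-sided 5% level. The primary PEG analysis and every decision rule are unaffected.

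**What to change.** In 15.4.2, for participant measures collected after classes start, choose one of two options.

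1. **Describe only.** Report the measures by arm without between-arm p-values, in line with Aim 3. This needs no extra work but gives up the tests.
2. **Model class.** Use linear or generalized linear mixed models with a class random effect. Preferably include session offering and between-class degrees of freedom, and add a participant random effect where months 2, 4 and 6 are combined. If class means or proportions are used instead, compare them paired within offering where both arms run in the same offering, because the unpaired test is conservative when offering effects are shared. The error-rate check above covers continuous class means only; the mixed models were not simulated.

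The text change is one or two sentences. Under option 2 at ICC 0.05 with 20% loss and nothing shared, the standard error rises by √D: about 11%, 16%, 21% and 26% for classes of 7, 10, 13 and 16. Multi-category measures need a little extra code. The same edit could usefully state whether the clustering approach in 15.3 applies to the responder, heterogeneity and mediation analyses.

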## 16 REGULATORY, ETHICAL, & STUDY OVERSIGHT

### 16.1 INFORMED CONSENT

#### 16.1.1 CONSENT & OTHER INFORMATIONAL DOCUMENTS

##### Community Stakeholder Information Sheet

Community Stakeholders (see Table 4) will be provided with an informational sheet prior to sharing their views and opinions. The information sheet details the names of the researchers, an explanation of what the community stakeholders will be expected to do and any risks associated with their involvement, and contact information for the IRB office and University of Minnesota in case of questions or concerns.

### Informed Consent Form (Study Participants)

The consent form will include, but is not limited to, the following: information regarding the study purpose and research design, study procedures, potential risks and benefits, alternatives to participation, voluntary nature of participation, privacy and confidentiality, research-related injury, disclosure of new information regarding participation, and who to contact outside the study in case of issues. Contact information for the PIs and project coordinator(s) will also be provided. Participants, study staff, and an impartial witness, as needed, will sign and date the consent form.

### Changes to the Informed Consent Form

In the event the informed consent form changes, following necessary IRB approvals, study staff will meet with the PI or designee and review changes to the form prior to conducting consent with new study participants. If existing study participants need to be informed of specific changes in the risks or benefits of study participation, an addendum consent will be used. This addendum will be used to, for example, inform enrolled participants about significant new findings that may have a bearing on their willingness to continue participation in the study. The addendum consent will be given to the participant at a study visit, emailed, or mailed to the participant's home.

## 16.1.2 CONSENT PROCEDURES & DOCUMENTATION

### Consent & Human Subjects Training

All research staff obtaining informed consent are required to undergo project specific human subjects training that addresses the essential components to the informed consent process. Staff responsible for consenting participants will be documented in the study's Delegation of Authority Log and in Ethos. In addition, staff will complete human subjects training in accordance with the UMN's human subjects and HIPAA training requirements.

This procedure establishes the process to obtain informed consent from participants. The process begins when an individual identifies as a potential candidate for the study and will continue throughout the duration of the study. The process ends when a participant declines consent to participate (e.g., prior to signing the consent, withdrawing consent) or when study completion occurs. Participants must demonstrate the ability to autonomously provide written or electronic consent. A Legally Authorized Representative (LAR) will not be used. The Principal Investigators are responsible for ensuring these procedures are carried out.

Potential participants will consent at 3 different time points: during a brief initial screening survey and at each of the two baseline screening appointments.

### Initial Screening Survey/Pre-Baseline Screening Visit

Interested individuals are initially screened using a web-based screening survey that can be completed independently online or over the phone with study staff. An overview of the study will be provided during the web-screen, and electronic consent secured prior to collecting preliminary information on eligibility (e.g., age, presence of chronic back or neck pain). Following the web-based screening, potential participants will be sent an informational video describing the study in more detail and will be contacted by study staff to answer any preliminary questions they may have (e.g., purpose of the study, interventions, time commitment) and schedule the first baseline screening appointment.

### Baseline 1 Screening Visit

This appointment can take place virtually or in-person at a participating study location. Prior to this appointment, participants will be given a copy of the consent document to review on their own. Study staff will verify the most current IRB-approved version of the consent form is used. Easy to understand, IRB pre-approved, electronic and print informational materials, including visual media, will be used to facilitate understanding of study procedures. As part of the informed consent process, potential research participants will be made aware of financial or business interests that may affect their decision to participate. None are anticipated; see Conflict of Interest Policy if a change in circumstance occurs. Study staff will review the consent form with the participants, section by section. This may be done one-on-one or in a group setting with other potential participants. Following review of the consent form, participants will be invited to ask questions one-on-one with study staff in a private and quiet space. Research staff will assess comprehension and understanding of information presented in the consent form using a series of open-ended questions (e.g., study purpose, interventions, risks). Participants will be encouraged to discuss taking part in the research study with family members, friends and/or healthcare providers, as appropriate. Participants are encouraged to think about study participation and will not be coerced or pressured into deciding to participate before they are ready. Written or electronic consent will be obtained from each study candidate. Only individuals who demonstrate comprehension will be considered eligible to participate. If the participant cannot read, an impartial witness can be used. The impartial witness must:

- Be present during the entire consent discussion to attest to the adequacy of the consent process and to the participant's voluntary consent. The witness must be present during the entire consent conversation, not just for signing the document(s).
- The witness may be a family member, friend, caregiver etc. The witness may not be a person involved in the design, conduct, or reporting of the research study.

All participants will be given a copy of the signed consent form for their personal records. Original signed paper consent forms will be secured in the respective participant's research file. Signed e-consent forms will be maintained in REDCap.

### Baseline 2 Screening Visit

At the second baseline screening visit, research staff will review the study purpose and procedures (e.g., study visits, data collection) and confirm continued consent to participate.

To complete the informed consent process at the end of study participation, study staff will inform the subject when their participation has ended and will document the discussion in the study record.

## **16.2 STUDY DISCONTINUATION & CLOSURE**

The study may be temporarily suspended or prematurely closed if there is sufficient reasonable cause. Written notification, documenting the reason for study suspension or termination, will be provided to study participants, investigators and study collaborators, funding agency, and regulatory authorities, including the UMN IRB, by the PIs or designee. In the event of any type of closure, the PIs, or designee, will promptly inform ongoing study participants, the IRB, and sponsor/funding agency and provide the reason(s) for the termination or temporary suspension.

Circumstances that may warrant termination or suspension include, but are not limited to:

- Determination of unexpected, significant, or unacceptable risk to participants

- Insufficient compliance of study staff to the protocol (i.e., significant protocol violations)
- Data that are not sufficiently complete and/or evaluable
- Major difficulties with study recruitment or retention
- Natural disaster, public health crisis

The study may resume once concerns about safety, protocol compliance, and data quality are addressed and satisfy regulatory bodies (e.g., funding agency, IRB, IMC).

